Prior treatment of acne, according to European treatment guidelines², will be assessed in the year prior to the index date (index date – 365 days, excluding index date; for included product names and ATC codes see Table 16.3 and Table 16.4 in Annex 2). Acne treatments will be classified as topicals, systemic preparations and hormonal agents and assessed separately for patients with and without an acne diagnoses in the year prior to index date. Because many of the drugs in the tables are not specific for acne, a pragmatic approach will be taken to select actual acne treatment in the study population: 1) select drugs by ATC or Gemscript code; 2) define dose and route of administration; 3) check with local guidelines for the approved indication of use and only include drugs that are approved for acne (alternative indications may exist). This check with the local guidelines is efficient because only the drugs that are actually used in the study population have to be checked once this data is available. Acne treatments will be further classified to whether it is only approved for acne, or also approved for other indications to allow sensitivity analysis.

Prior diagnoses of hyperandrogenic conditions or medical conditions where EE/progestin combinations are prescribed for frequently will be assessed in the year prior to index date (index date – 365 days, excluding index date; for included codes, see Table 16.5 and Table 16.6):

- Acne
- Alopecia
- Contraceptive management
- Hirsutism
- Menstrual problems
- Oligomenorrhoea/amenorrhoea
- Polycystic ovary syndrome (PCOS)
- Seborrhoea

For the 2017 study extension the following will be assessed:

Demographic characteristics:

- Age at index date (in years, categorized, mean (\pm SD), median (IQR))
- History available prior to the index date (in years, categorized, mean (\pm SD), median (IQR))
- Follow-up available after the index date (in months, categorized, mean (\pm SD), median (IQR))

Concomitant use of hormonal contraceptives:

- Number of CPA/EE treatment episodes (categorized, mean (\pm SD), median (IQR))
- Summed duration of CPA/EE use (in months, categorized, mean (\pm SD), median (IQR))
- Concomitant use of hormonal contraceptives (concomitant, potential concomitant, non-concomitant or no use of hormonal contraceptives)
- Duration of concomitant use of CPA/EE and hormonal contraceptives (≤ 28 days concomitant use, $>28 - 84$ days concomitant use or >84 days concomitant use, mean (\pm SD), median (IQR))

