| 97118997 | Erythromycin 500mg ec gastro-resistant tablets |
| 97121990 | Doxycycline 100mg capsules |
| 97209989 | Doxycycline 100mg capsules |
| 97246992 | Doxycycline 100mg capsules |
| 97361997 | Erythromycin stear 500mg tabs |
| 97381992 | Erythromycin stear 500mg tabs |
| 97559997 | Minocycline 100mg tablets |
| 97559998 | Minocycline 50mg tablets |
| 97738989 | Minocycline 100mg tablets |
| 97738990 | Minocycline 50mg tablets |
| 97761989 | Doxycycline 100mg capsules |
| 97913998 | Doxycycline 100mg tablets |
| 98029989 | Minocycline 100mg tablets |
| 98029990 | Minocycline 50mg tablets |
| 98044990 | Doxycycline 100mg capsules |

| | |
|----------|--|
| 98166989 | Erythromycin 500mg ec gastro-resistant tablets |
| 98231998 | Doxycycline 100mg disp tabs |
| 98345990 | Erythromycin 500mg ec gastro-resistant tablets |
| 98352990 | Doxycycline 100mg capsules |
| 98480989 | Minocycline 100mg tablets |
| 98530998 | Minocycline 100mg m/r capsules |
| 98531996 | Minocycline 100mg capsules |
| 98531997 | Minocycline 50mg capsules |
| 98531998 | Minocycline 100mg modified-release capsules |
| 98558990 | Erythromycin 500mg ec gastro-resistant tablets |
| 98601989 | Doxycycline 100mg capsules |
| 98751997 | Erythromycin 500mg/sach grans |
| 98752998 | Erythromycin 500mg e/c tablet |
| 98754998 | Erythromycin stear 500mg tabs |
| 98969997 | Doxycycline 100mg disp tabs |
| 98969998 | Doxycycline 100mg capsules |
| 99054998 | Lymecycline 408mg capsules |
| 99101998 | Doxycycline 100mg capsules |
| 99103996 | Erythromycin 500mg e/c tablet |
| 99210990 | Erythromycin 500mg ec gastro-resistant tablets |
| 99433990 | Erythromycin 500mg ec gastro-resistant tablets |
| 99434990 | Erythromycin 500mg ec gastro-resistant tablets |
| 99435989 | Erythromycin 500mg ec gastro-resistant tablets |
| 99542997 | Erythromycin stear 500mg tabs |
| 99613990 | Doxycycline 100mg capsules |
| 99683997 | Erythromycin 500mg e/c tablet |

Table 16.5 Codes of diagnoses of hyperandrogenic conditions during the year before index date for PHARMO and HSD

| Diagnosis* | ICD-10 | ICD-9(-CM) | ICPC |
|-----------------------------|------------------|---|------------------|
| Acne | L70 | 706.0, 706.1 | S96 |
| Alopecia | L63-L66 | 704.0 | S23 |
| Contraceptive management | Z30.01 | V25.01, V25.02, V25.05 | W11-W12 |
| Hirsutism | L68.0 | 704.1,757.4 (incl. sub code 59 for HSD) | S24.01 |
| Menstrual problems | N92, N94.3-N94.9 | 626.1, 626.2, 626.4, 626.8, 626.9 | X02-X03, X06-X09 |

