| Oligomenorrhoea/amenorrhoea | N91 | 626.0, 626.1 | X05 |
| PCOS | E28.2 | 256.4 | T99.06 |
| Seborrhoea | L21 | 706.3 | S86 |

*all diagnoses will be based on episode text mining in GP episodes as well; PCOS = polycystic ovary syndrome.

Table 16.6 Read codes of diagnoses of hyperandrogenic conditions or conditions EE/progestin combinations are prescribed for frequently during the year before index date for THIN

| Read code | Descriptor |
|--------------------------|---------------------------------|
| Acne | |
| 2FG5.00 | Acne scar |
| M153000 | Acne rosacea |
| M26..00 | Sebaceous gland diseases |
| M260.00 | Acne varioliformis |
| M260000 | Acne frontalis |
| M260z00 | Acne varioliformis NOS |
| M261.00 | Other acne |
| M261000 | Acne vulgaris |
| M261100 | Acne conglobata |
| M261600 | Cystic acne |
| M261A00 | Pustular acne |
| M261E00 | Acne excoriee des jeunes filles |
| M261F00 | Acne fulminans |
| M261X00 | Acne, unspecified |
| M261z00 | Other acne NOS |
| Myu6800 | [X]Other acne |
| Myu6F00 | [X]Acne, unspecified |
| Alopecia | |
| 1N02.00 | C/O: hair loss |
| 22D4.00 | O/E - loss of hair |
| 22D7.11 | O/E - alopecia |
| M240.00 | Alopecia |
| M240000 | Alopecia unspecified |
| M240011 | Baldness |
| M240012 | Hair loss |
| M240200 | Male pattern alopecia |
| M240z00 | Alopecia NOS |
| Contraceptive management | |
| 61...00 | Contraception |
| 614..11 | Oral contraception |
| 614..12 | Pill - oral contraception |
| 6145.00 | Oral contraception -no problem |
| 614Z.00 | Oral contraception NOS |
| 61X..00 | Planned contraception method |
| 61Y..00 | Uses contraception |
| 61Z..00 | Contraception NOS |
| 6777.00 | Contraception counselling |
| 6147.00 | Combined oral contraceptive |

| | |
|---------|--|
| 67Ij.00 | Advice to GP to change pt oral contraceptive from combined |
| 1561.00 | H/O: oral contraceptive usage |
| 1561000 | H/O: progestogen only oral contraceptive usage |
| 614..00 | Oral contraceptive |
| 614..11 | Oral contraception |
| 614..12 | Pill - oral contraception |
| 6141.00 | Oral contraceptive started |
| 6142.00 | Oral contraceptive stopped |
| 6143.00 | Oral contraceptive re-started |
| 6144.00 | Oral contraceptive repeat |
| 6145.00 | Oral contraception -no problem |
| 6146.00 | Oral contraception - problem |
| 6146100 | Headache caused by oral contraceptive pill |
| 6146200 | Hypertension induced by oral contraceptive pill |
| 6147.00 | Combined oral contraceptive |
| 6148.00 | Progestagen only oral contraceptive |

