| K59yy00 | Functional uterine haemorrhage NOS |

| | |
|-----------------------------|--|
| K59z.11 | Break - through bleeding |
| 1574.00 | H/O: dysmenorrhoea |
| Eu45y11 | [X]Psychogenic dysmenorrhoea |
| K582.00 | Mittelschmerz - ovulation pain |
| K583.00 | Dysmenorrhoea |
| K583.11 | Painful menorrhoea |
| K583.12 | Painful menstruation |
| K583.13 | Period pains |
| K583.14 | Spasmodic dysmenorrhoea |
| K583000 | Primary dysmenorrhoea |
| K583100 | Secondary dysmenorrhoea |
| 1572.00 | H/O: polymenorrhoea |
| 158..00 | H/O: abnormal uterine bleeding |
| 158..12 | Vaginal bleeding |
| K56y111 | Bleeding - vaginal NOS |
| K56y112 | BPV - Vaginal bleeding |
| K592.11 | Frequent menses |
| K59y300 | Intermenstrual bleeding |
| K594.00 | Irregular menstrual cycle |
| K594000 | Delayed period |
| K594011 | Late period |
| K594z00 | Irregular menstrual cycle NOS |
| 1573.00 | H/O: menorrhagia |
| K5A0.00 | Premenopausal menorrhagia |
| K5A0.11 | Climacteric menorrhagia |
| K5A6.00 | Perimenopausal menorrhagia |
| 158..00 | H/O: abnormal uterine bleeding |
| 1584.00 | Heavy episode of vaginal bleeding |
| K592.00 | Excessive or frequent menstruation |
| K592z00 | Excessive or frequent menstruation NOS |
| K59y.00 | Other menstruation disorders |
| K59yz00 | Other menstruation disorder NOS |
| K592000 | Menorrhagia |
| K59y000 | Retained menstruation |
| K594012 | Delayed menstruation |
| Oligomenorrhoea/amenorrhoea | |
| 1571.00 | H/O: amenorrhoea |
| K590.00 | Absence of menstruation |
| K590.11 | Amenorrhoea |
| K590000 | Primary amenorrhoea |
| K590100 | Secondary amenorrhoea |
| K590111 | Post-pill amenorrhoea |

| | |
|------------|---------------------------------------|
| K590z00 | Amenorrhoea NOS |
| K591.00 | Scanty or infrequent menstruation |
| K591.11 | Infrequent menstruation |
| K59y100 | Suppression of menstruation |
| 1571.00 | H/O: amenorrhoea |
| K590.00 | Absence of menstruation |
| K590111 | Post-pill amenorrhoea |
| K591000 | Hypomenorrhoea |
| K591100 | Oligomenorrhoea |
| K591200 | Primary oligomenorrhoea |
| K591300 | Secondary oligomenorrhoea |
| K591z00 | Scanty or infrequent menstruation NOS |
| PCOS | |
| C164.00 | Polycystic ovaries |
| C164.11 | Isosexual virilisation |
| C164.12 | Stein - Leventhal syndrome |
| C164.13 | Multicystic ovaries |
| C165.00 | Polycystic ovarian syndrome |
| C16y.00 | Other ovarian dysfunction |
| Seborrhoea | |
| M263.00 | Seborrhoea |
| M263000 | Seborrhoea corporis |

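### The THIN acne code list in Table 16.6 includes rosacea and two non-specific codes, which overstates the acne flag by an unknown, probably small amount

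*Protocol*

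**What the plan says.** Table 16.6 (Annex 3) lists the Read codes that define each diagnosis in THIN. Among the 17 entries under acne are "M153000 | Acne rosacea", "M26..00 | Sebaceous gland diseases" and "2FG5.00 | Acne scar". The same table gives seborrhoea its own category, starting with "M263.00 | Seborrhoea".

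For PHARMO and HSD, Table 16.5 defines the two conditions as "Acne | L70 | 706.0, 706.1 | S96" and "Seborrhoea | L21 | 706.3 | S86". A footnote to Table 16.5 adds that every diagnosis will also be sought by text mining of GP episodes. It states no search terms and no exclusions.

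The acne flag is used twice. It gives the acne row of Tables 14.7 and 14.8. It also splits the acne-treatment tables (14.5 and 14.6), because under section 9.3 prior acne treatment is "assessed separately for patients with and without an acne diagnoses in the year prior to index date".

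**The concern.** Section 9.9 says that the indication for most prescriptions has to be inferred from recorded diagnoses, and section 7 names acne as one of the two conditions for which the product should be used. The acne flag is therefore the study's main evidence on why these women received CPA/EE.

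A code that does not identify acne can only add women to the flag. It raises the THIN acne row and moves women from the half of Tables 14.5 and 14.6 without an acne diagnosis into the half with one. Section 9.3 concedes that many of the listed drugs are not specific to acne, so the diagnosis split is what helps the reader tell acne treatment from other use. A woman whose only code is rosacea and who received one of the listed antibiotics would be counted as an acne patient with prior acne treatment.

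**Working it through.** **Step 1: sort the 17 THIN acne codes in Table 16.6.**
- M260 branch: 3 codes (M260.00, M260000, M260z00).
- M261 branch: 9 codes (M261.00, M261000, M261100, M261600, M261A00, M261E00, M261F00, M261X00, M261z00).
- Myu6: 2 codes (Myu6800, Myu6F00).
- Outside these: 3 codes (M153000, M26..00, 2FG5.00).

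The total is 3 + 9 + 2 + 3 = 17, and 14 remain without the three.

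**Step 2: judge the three codes one by one.**
- M153000 is rosacea. It lies in M15, outside the M26 block that holds the acne disease codes. This is the clear misfit.
- M26..00 is the head of a block that contains acne (M260, M261) and seborrhoea (M263). Since the table reports seborrhoea separately, its own structure shows that this code cannot tell the two apart. As printed it is a single code, not a wildcard, and it may hold some true acne.
- 2FG5.00 records a scar. It may follow past acne and does not place active acne in the year before the index date, but it may accompany true acne.

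**Step 3: compare with Table 16.5.** The acne entries there are L70, 706.0, 706.1 and S96. Code 706.3 is kept apart as seborrhoea, and the 706 parent is not listed. No entry corresponds to the three THIN codes. Table 16.5 prints no descriptors for individual codes, so this comparison goes no further than what is listed.

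**Step 4: size.** The protocol gives no THIN acne count and no count per code, so there is no stated figure to reproduce. For illustration, let p be the share of THIN starters flagged as acne and s the share of those flagged only through the three codes. Removing all three lowers the acne share by p × s. Both inputs are assumptions: p = 30% to 60%, s = 1% to 10%.
- Low end: 0.30 × 0.01 = 0.3 percentage points.
- High end: 0.60 × 0.10 = 6.0 percentage points.

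With the numbers of starters in Table 15.2:
- 2011 (N = 2,760): 8 to 166 women.
- 2012 (N = 2,923): 9 to 175 women.
- 2014 (N = 2,341): 7 to 140 women.

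This counts every woman flagged only by these codes as misclassified, so it is an upper reading for each s.

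**Step 5: effect on the treatment split.** Suppose that 80% of true acne cases had prior acne treatment and a share t of the added women did (assumed t = 20% to 80%). The treated share in the stratum with an acne diagnosis then reads (1 − s) × 80% + s × t.
- s = 1%: 0.99 × 80% + 0.01 × 20% = 79.4%, rising to 80.0% at t = 80%.
- s = 10%: 0.90 × 80% + 0.10 × 20% = 74.0%, rising to 80.0% at t = 80%.

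**The case against.** A reader might infer that the error sits in THIN alone and so biases the comparison between databases. The documents do not support that. Free text that mentions acne rosacea or acne scars contains the word acne, and the text mining under Table 16.5 could pick it up. Without stated terms, neither its presence nor its absence in PHARMO and HSD can be shown. No formal contrast between databases is planned either: the secondary objective in section 8.1 compares 2011/2012 with 2014, and the analysis is descriptive. The tables do, however, set the databases side by side.

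A reader might also infer that an on-label share is inflated. The protocol defines no such measure. Tables 14.7 and 14.8 list eight diagnoses, and the label concerns moderate to severe acne, a severity that the acne row does not measure.

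Three further objections carry weight:
- Dropping the parent and scar codes trades sensitivity for specificity, and section 9.9 already warns of under-recorded diagnoses. This stands for those two codes, not for rosacea.
- Section 9.3 restricts treatments to drugs approved for acne and separates those with other indications for a sensitivity analysis. This helps with the treatments but leaves the diagnosis flag as it is. The note that a list is preliminary stands under Table 16.3, on treatments, and not under Table 16.6.
- The affected runs were due for final report in March 2016, and the extension contains no diagnosis analysis. This bears on how the correction is reported, not on whether the list is right.

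**Conclusion.** The point holds in limited form. Table 16.6 fixes an acne definition that includes one different disease and two codes that cannot identify current acne by themselves. The result is an upward misclassification in the THIN acne row and in the split by acne diagnosis, for 2011, 2012 and 2014.

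Its size is unknown. The range of 0.3 to 6.0 percentage points rests wholly on the assumed p and s. That the low end is more likely is a judgement, based on the mean age of 23 years among THIN starters (Table 15.2) and on the chance that some of the added women do have acne.

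The same list applies in every year, so the comparison of 2011/2012 with 2014 is less exposed than the THIN level, provided that coding habits were stable. Concomitant use and the 2015–2017 extension do not use the flag and are untouched.

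**What to change.** - Remove M153000 from the THIN acne definition in Table 16.6.
- Take M26..00 and 2FG5.00 out of the main definition. Show women who have only these codes on a separate line, and give a sensitivity result that counts them as acne.
- State the text-mining terms used under Table 16.5 and apply the same exclusion of rosacea there.
- Rerun the THIN acne row and the split of the treatment tables for 2011, 2012 and 2014. If those results have already been reported, give the revised figures as a sensitivity line instead of reopening the report.

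The cost is a code-list edit, a rerun of one flag in THIN and a check of the text-mining terms for PHARMO and HSD. The downside is that a few women with true acne, coded only under the parent or scar code, move to the separate line; the sensitivity result keeps them visible.

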Cyproterone acetate (CPA) 2mg, in combination with ethinylestradiol (EE) 35mcg is a medicinal product currently indicated for the treatment of moderate to severe acne and/or for hirsutism in women of reproductive age. Androgen-dependent symptoms such as acne, hirsutism, seborrhea, and alopecia, as well as androgen sensitivity-related symptoms of Polycystic Ovary Syndrome (PCOS) have been considered as potential therapeutic targets for CPA. Due to the mode of action and the dose and regimen, the preparations also act as effective contraceptives. Market authorization was first granted in 1985.

A review of CPA/EE was triggered by the French medicines agency, the National Agency for the Safety of Medicine and Health Products (ANSM), following its decision to suspend CPA/EE in France within three months in January 2013. The French decision followed a national review of the medicine by ANSM. The Coordination Group for Mutual Recognition and Decentralised Procedures – Human (CMDh) endorsed the recommendation of the European Medicines Agency’s Pharmacovigilance Risk Assessment Committee (PRAC), which concluded that the benefits of CPA/EE (cyproterone acetate 2mg / ethinylestradiol 35mcg) outweigh the risks, provided that several measures are taken to minimize the risk of thromboembolism. These medicines should be used solely in the treatment of moderate to severe acne related to androgen sensitivity and/or hirsutism in women of reproductive age. Furthermore, CPA/EE should only be used for the treatment of acne when alternative treatments, such as topical therapy and antibiotic treatment, have failed.

Since CPA/EE also acts as a hormonal contraceptive, women should not take this medicine in combination with a hormonal contraceptive. The concomitant use of CPA/EE with a hormonal contraceptive would expose women to a higher hormonal dose and therefore potentially increase the risk of thromboembolism.

During the referral procedure, the risk of thromboembolism occurring with CPA/EE was assessed as low and well known. However, to minimize this risk, the respective MAHs were required to implement further measures in addition to updating the product information, provide educational materials to prescribers and patients highlighting the risks of thromboembolism¹ and to conduct drug utilization and post authorisation safety studies.

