| 8CAw200 | Written advice about long acting reversible contraception |
| 8CED.00 | Emergency contraception leaflet given |
| 8CEE.00 | Contraception leaflet given |
| 8CEF.00 | Intrauterine device contraception leaflet given |
| 8CEG.00 | Long acting reversible contraception leaflet given |
| 961..11 | FP1001 - contraception claim |
| 98CA.00 | GMS4 claim - contraception (non IUCD) signed |
| 98CB.00 | GMS4 claim - contraception (non IUCD) sent to HA |
| 98CC.00 | GMS4 claim - contraception (non IUCD) up to date |
| 98CD.00 | GMS4 claim - contraception (non IUCD) due |
| 98CE.00 | GMS4 claim - contraception (non IUCD) due next visit |
| 98CF.00 | GMS4 claim - contraception (non IUCD) cancelled |
| 98CG.00 | GMS4 claim - contraception (non IUCD) not claimed |
| 98CH.00 | GMS4 claim - contraception (non IUCD) forgot to claim |

| | |
|---------------------------|---|
| 98CI.00 | GMS4 claim - contraception (non IUCD) paid |
| 98CJ.00 | GMS4 claim - contraception (non IUCD) returned unpaid |
| 98CK.00 | GMS4 claim - contraception (IUCD) signed |
| 98CL.00 | GMS4 claim - contraception (IUCD) sent to HA |
| 98CM.00 | GMS4 claim - contraception (IUCD) due with new IUCD |
| 98CN.00 | GMS4 claim - contraception (IUCD) paid |
| SP03217 | Contraception IUCD causing bleeding |
| ZV15700 | [V]Personal history of contraception |
| Hirsutism | |
| M241.00 | Hirsutism - hypertrichosis |
| M241.11 | Polytrichia |
| M241100 | Idiopathic hypertrichosis |
| M241200 | Hypertrichosis lanuginosa (acquired) |
| M241400 | Hypertrichosis partialis |
| M241500 | Hypertrichosis universalis |
| M241600 | Polytrichia |
| M241z00 | Hypertrichosis NOS |
| Menstrual problems | |
| K584.00 | Premenstrual tension syndrome |
| K584.11 | Migraine - menstrual |
| 1573.11 | H/O: heavy periods |
| K592.00 | Excessive or frequent menstruation |
| K592.11 | Frequent menses |
| K592.12 | Hypermenorrhoea |
| K592000 | Menorrhagia |
| K592011 | Heavy periods |
| K592100 | Polymenorrhoea |
| K592111 | Epimenorrhoea |
| K592z00 | Excessive or frequent menstruation NOS |
| K593.00 | Puberty bleeding |
| K593.11 | Pubertal bleeding and menorrhagia |
| K595.00 | Ovulation bleeding |
| K595.11 | Intermenstrual bleeding - regular |
| K596.00 | Metrorrhagia |
| K596.11 | Intermenstrual bleeding - irregular |
| K598.00 | Menometrorrhagia |
| K599.00 | Mid-cycle bleeding |
| K59y.11 | Metropathia haemorrhagica |
| K59yx00 | Dysfunctional uterine haemorrhage NOS |
| K59yx11 | Dysfunctional uterine bleeding |

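### The THIN code lists for hirsutism and PCOS in Table 16.6 are wider than their labels and not harmonised with Table 16.5, so the side-by-side diagnosis rows are not ascertained alike (minor)

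*Protocol*

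**What the plan says.** Section 8.1 makes previous diagnosis of acne, hirsutism or other hyperandrogenic conditions one of the main objectives. Section 7 gives hirsutism, with acne, as an indication and places it among the symptoms that depend on androgens: "Androgen-dependent symptoms such as acne, hirsutism, seborrhea, and alopecia". Section 9.3 points to Tables 16.5 and 16.6 for the codes. Tables 14.7 and 14.8 report hirsutism and PCOS as single rows with PHARMO, THIN and HSD in adjacent columns.

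For THIN, Table 16.6 opens the hirsutism list with "M241.00 | Hirsutism - hypertrichosis" and continues with seven further codes, among them "M241200 | Hypertrichosis lanuginosa (acquired". Its PCOS list has six codes, the last being "C16y.00 | Other ovarian dysfunction".

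For PHARMO and HSD, the hirsutism row of Table 16.5 reads "Hirsutism | L68.0 | 704.1,757.4 (incl. sub code 59 for HSD) | S24.01" and the PCOS row reads "PCOS | E28.2 | 256.4 | T99.06". A footnote to that table adds that "all diagnoses will be based on episode text mining in GP episodes as well". Table 16.6 has no such footnote.

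**The concern.** A row headed hirsutism should count women with a record of hirsutism, and a row headed PCOS women with a record of PCOS. The THIN lists admit terms that by their own wording describe something else: hair growth terms that do not mention hirsutism, and an ovarian category defined by being other than the named ones.

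Hirsutism is one of the two indications given in section 7, so readers will use that row to judge whether prescribing followed the indication. Two columns under one label also invite a comparison between countries. If the columns rest on different definitions, part or all of a visible difference could come from the code lists.

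**Working it through.** No figure in the plan can be reproduced here, because the protocol gives no counts by diagnosis code. The check sets the lists side by side and then scales the possible effect.

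**1. Hirsutism in THIN (Table 16.6).** Eight codes are listed.
- One names hirsutism, as a joint term: M241.00.
- Five name hypertrichosis only: M241100, M241200, M241400, M241500, M241z00.
- Two name polytrichia only: M241.11, M241600.

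So 5 + 2 = 7 of 8 codes do not mention hirsutism, and no listed code is for hirsutism alone.

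**2. PCOS in THIN (Table 16.6).** Six codes are listed: C164.00, C164.11, C164.12, C164.13, C165.00 and C16y.00. The last is a residual category. C164.11 (isosexual virilisation) and C164.13 (multicystic ovaries) do not spell out PCOS either, but they sit under the polycystic ovaries code C164. C16y.00 does not.

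**3. The same rows in Table 16.5.**

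| Condition | ICD-10 | ICD-9(-CM) | ICPC | Extra route |
|---|---|---|---|---|
| Hirsutism | L68.0 | 704.1 and 757.4, with sub code 59 for HSD | S24.01 | text mining |
| PCOS | E28.2 | 256.4 | T99.06 | text mining |

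PCOS has one code per coding system and no residual category. Hirsutism has one ICD-10 code and one ICPC code, but two ICD-9 codes. Table 16.5 prints no descriptor for individual codes, so the document does not show how broad 704.1 and 757.4 are. The footnote covers all diagnoses, but it does not say whether HSD is text mined as PHARMO is.

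**4. Effect within THIN.** Let f be the share of women flagged in a THIN row who qualify only through the non-specific codes. Row as planned divided by row without those codes = 1/(1-f). The values of f are assumptions.

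| f | 1/(1-f) |
|---|---|
| 0 | 1.00 |
| 5% | 1/0.95 = 1.05 |
| 20% | 1/0.80 = 1.25 |
| 50% | 1/0.50 = 2.00 |

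Extra codes can only raise the THIN row or leave it unchanged relative to a shorter THIN list. For hirsutism the comparison row still holds the joint code M241.00, so it is not a pure hirsutism count.

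**5. Scale in women.** Table 15.2 gives 2,341 THIN starters in 2014. If the hirsutism row stood at an assumed 5%, it would hold 0.05 × 2,341 = 117 women. At f=20%, 0.20 × 117 = 23 would move to a separate line and 94 would remain, or 94/2,341 = 4.0%.

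**6. Effect on the period comparison.** If the excess is the same in each year, the absolute change is unaffected and the ratio is diluted. An assumed true rise from 4% to 6% (ratio 1.50) with 2 points added in both periods becomes 6% to 8% (ratio 1.33). The difference stays at 2 points.

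**The case against.** Several stronger readings are tempting, and the document does not support them.

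- **That PHARMO rests on one exact sub-code per condition.** The ICPC column alone suggests it, but the Table 16.5 footnote adds text mining, and section 9.4.1 says that PHARMO diagnoses can also be entered as free text. Text mining can raise PHARMO counts.
- **That THIN is overstated relative to PHARMO or HSD.** The direction is open. Text mining works against it for PHARMO, and for HSD the hirsutism row has two ICD-9 codes of unstated breadth.
- **That seven of eight codes means a large error.** This counts codes and not women. A woman with M241.00 is counted whatever else is listed, and the other seven may be rarely used.
- **That gaps in the Read numbering show a missing hirsutism code.** The dictionary is not in the document, so nothing follows. If such a code existed, the row could also miss true cases.
- **That an on-label share is inflated.** No such variable is defined.

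There is also a fair defence of the plan. Where the heading term itself merges hirsutism and hypertrichosis, a broad list is a reasonable choice of sensitivity over specificity. The formal secondary objective compares periods and not countries. Section 6 has separate database results compiled in one document. Section 9.9 already warns that indication depends on recorded diagnoses. Tables 15.1 to 15.3 carry results for 2011, 2012 and 2014, so those runs appear complete, and the 2015-2017 extension assesses no diagnoses.

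These arguments lower the weight of the point and rule out any claim about direction. They do not justify a residual ovarian code under a PCOS label, and they do not make the adjacent columns one measure.

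**Conclusion.** The point holds as a minor one. The THIN hirsutism and PCOS rows are over-inclusive relative to their labels by an unknown amount, possibly negligible. The columns of Tables 14.7 and 14.8 are not ascertained in the same way, since both the code lists and the use of text mining differ. This rests only on the descriptors in Table 16.6 and the contents of Table 16.5. The factors of 1.00 to 2.00 illustrate an assumed range and are not estimates.

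A reader might go on to conclude that THIN overstates hirsutism or PCOS against the Netherlands or Italy. That does not follow: the sign of a THIN-PHARMO or THIN-HSD difference cannot be determined from the protocol. The 2011/2012 versus 2014 contrast within THIN is affected less than the level, provided the same list is used throughout.

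**What to change.** - In Table 16.6, remove C16y.00 from the THIN PCOS row, or report women who qualify only through it on their own line.
- Label the THIN row based on M241.00 as hirsutism/hypertrichosis (joint code). Report women who qualify only through M241.11, M241100 to M241600 or M241z00 on a separate line, hypertrichosis only.
- Footnote Tables 14.7 and 14.8 to say that code lists and text mining differ between the databases, and state in Table 16.5 whether text mining applies to PHARMO, HSD or both.

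The change concerns the 2011, 2012 and 2014 diagnosis rows only and leaves the 2015-2017 extension untouched. It costs a rerun of two THIN flags in analyses that appear already done, and needs no new data. True hirsutism that a GP coded as hypertrichosis would move to the separate line, where it stays visible. The joint code still cannot be split, which is why the label has to change. If the separate lines turn out to be nearly empty, that count settles the matter.
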